**d. Statistical Power and Sample Considerations**

*Analyses for Aim 1:*

Aim 1: To evaluate the effects of a data-driven HOT management protocol on parent(s) quality of life.	Hypothesis 1.1: Parents of patients weaned from HOT using a data-driven management protocol will have improved quality of life compared to their status at time of NICU discharge compared to patients weaned using the current standard HOT management protocol.
--	--

For the impact of oxygen management protocol on the family's emotional health, we will use the PedsQL. We are performing these scales at the beginning of the outpatient HOT management process, to establish a baseline, and then will repeat these measures at the end of the HOT weaning process (6 months after discontinuation of HOT). We will test the association of oxygen management protocol with change in each measure using the Student's *t*-test to analyze the difference between intervention groups. Multivariate linear regression models will adjust for potential confounding variables, including parent and medical attributes.

Power calculation for hypothesis 1.1:

Power calculations are based on the primary analyses (t-test). A sample size of 130 will give 80% power, with 0.05 two-sided type I error rate, to detect a 20% absolute difference in emotional role limitation on the PedsQL, which we consider to be clinically significant.

*Analyses for Aim 2:*

Aim 2: To evaluate the impact of a data-driven HOT management protocol on duration of HOT.	Hypothesis 2.1: A data-driven HOT protocol will shorten duration of HOT therapy compared to the current standard HOT management protocol.
---	--

For the primary outcome, duration of HOT, the interval from date of first outpatient clinic visit/enrollment to discontinuation of HOT will be determined. Mean duration of HOT between the two groups will be compared.

Based on our experience weaning over 130 premature infants from O2, we expect the mean duration of HOT in our standard treatment group (clinic-based weaning) to be 144+/-66 days, and we anticipate that RHO weaning strategies will decrease the median duration by 25% (36 days) to 108 days. A total sample of 98 infants per group provides 97% power to detect this effect of the RHO strategy (two-tailed, alpha=0.05, see Table 2).

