Parents of all infants will be asked to complete a structured quality-of-life survey, the PedsQL Family Impact Module (PedsQL), at their initial (baseline) clinic visit, and monthly at each clinic visit until the infant is weaned. A follow-up PedsQL will be done 3 months after weaning either by phone or at a clinic visit. Health care utilization (emergency department visits and rehospitalizations) and information on growth and nutrition will be assessed at monthly clinic visits while the child is on oxygen, as well as 1 and 6 months after discontinuation of oxygen. Additionally, post-wean, but before their 6 month follow-up, parents of Arm B children will be approached in clinic, or contacted via phone, to collect a brief, 5 minute Home Oximetry Feasibility Questionnaire survey that helps to identify variables that may correlate with an increased or decreased likelihood to record and send home oxygen data.

Our overall objective is to determine whether RHO can improve caregiver quality of life, and can shorten HOT duration and eliminate need for PSG, without compromising safety. We will determine respiratory-related re-hospitalizations, emergency department (ED) visits, and growth parameters to confirm safety of the proposed weaning strategies.

Our specific aims include: **Specific Aim 1:**

**To evaluate the impact of a data-driven HOT management protocol on duration of HOT.** *We hypothesize that RHO will shorten duration of HOT therapy compared to the current standard HOT management protocol* **Specific Aim 2: To evaluate the effects of a data-driven HOT management protocol on parent quality of life.** *We hypothesize that RHO utilization will decrease emotional and financial stress compared to standard oxygen management approaches.*

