#### **4.d. Description of Study Treatments or Exposures/Predictors**

All participants will have the following study treatments:

1. Parents of enrolled infants will have parent reports/surveys to assess quality of life using the **PedsQL** at each monthly clinic visit until the infant has weaned and a 3 month post weaning follow-up PedsQL report/survey either by phone or in clinic.
2. All infants will have **growth assessments** at each monthly clinic visit before and after the wean.
3. **Nutrition regimen** will also be collected at each monthly clinic visit, and the 1 month and 6 month post-wean follow-up visits to capture factors that contribute to growth. Nutrition information will include any note on nutrition regimen made by a physician or nutritionist at the time of visit.
4. All infants will have **monthly clinic visits** with O2 challenges in clinic until oxygen is discontinued. (\*\*This is standard clinical care and not a separate research treatment)
5. Infants in Arm A ("Standard" management) will have **polysomnogram** performed prior to discontinuation of HOT. (This is a clinically-indicated, although not mandatory test). They will have RHO on the night prior to and during the polysomnogram.
6. Infants in Arm B (RHO) will use an **additional oximeter to record data** and will transmit the data every 4-7 days to research staff.
7. Parents of infants in ARM B (RHO) will also be given a **post study Home Oximetry Feasibility Questionnaire** to complete. This is a questionnaire that will be used to determine the advantages and challenges of using home oximetry. This questionnaire would be conducted at the 1 month post-wean visit, however, if unable to obtain at this time point, due to missed visit or lost to follow-up it can be collected post wean at any time at a clinic visit or over the phone.

*\*For patients in ARM B who have completed the study and have not completed the Home Oximetry Feasibility Questionnaire, this will be obtained from the parents retrospectively by sending them a letter and the questionnaire or by calling and obtaining verbal consent to conduct the questionnaire before doing so. Additionally, for all past patients, nutrition notes will also be obtained for the clinic visits that they attended during the course of the study.*

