#### **4.e. Definition of Primary and Secondary Outcomes/Endpoints**

Primary measures: (a) Total duration of home oxygen therapy (HOT) from the first outpatient pulmonary appointment to discontinuation of supplemental O2; and (b) Parent quality of life, assessed by differences in the post-weaning PedsQL baseline.

Secondary measures: (a) Number of rehospitalizations and emergency department visits from 1st clinic visit through 6 months after discontinuation of HOT; (b) Change in weight and weight-for-length z-score from 1st clinic visit to 6 months after discontinuation of HOT; and (c) For patients who will receive a sleep study, percent time below designated O2 saturation thresholds (<96%, <93%, and < 90%) will be calculated from both RHO and from the polysomnogram data. The number of desaturation events (defined as saturation drops below 90% for >10 seconds and > 20 seconds) will also be analyzed.

Duration of HOT was chosen as a primary outcome since it is the primary driver of caregiver emotional and financial health for families of infants on HOT. This outcome was driven by input from families themselves, through a process of including important stakeholders in the protocol development process. The PedsQL was chosen as an additional primary outcome because it is validated, accurate scale in which scores correlate with maternal psychiatric symptoms, poor child health, poor child adjustment, and increased child hospitalizations.

This protocol focuses on patient-centered outcomes that may demonstrate non-inferiority from a medical safety perspective, but may improve quality of life. While families place a priority on treatment strategies that optimize health, when there are multiple choices without a clear medically superior choice, then the impact of specific treatment choices on quality of life will help drive decision-making.

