##### **Informed Consent:**

Consent for this study at BCH will be obtained by the site PI or study team.

Consent will be obtained at the first study visit at all sites. Adequate time will be allowed between the review of the consent form and the signing of the consent form to allow families to decide on their participation. We will gauge the parents' level of understanding by asking them questions about the various elements of the consent. Significant new findings during the course of the research would require changes to the informed consent document. Subjects would be re-consented with the new approved

consent form at their next study visit, prior to any procedures being performed. Because at BCH we feel it will be important for other healthcare providers to know if the child is participating in this study, the consent forms will be placed in the subjects BCH medical record.

ARMA										Follow-up					
Study Period		Baseline (Initial Visit)					Follow-up								
Visit	V0	V1	–	V2	–	V3	–	V4	–	V5	1 mo post wean	–	3 mo post wean	–	6 mo post wean (Final visit)
Consent	X														
Eligibility Criteria	X														
NICU Discharge Summary	X														
Clinic O2 Setting	X	X	X	X	X	X	X	X	X						
PedsQL	X	X	X	X	X	X	X	X	X			X			
Growth Assessment	X	X	X	X	X	X	X	X	X					X	
PSG															
AE/ED/Rehospitalizations			X	X	X	X	X	X	X			X			X
Nutrition Assessment	X	X	X	X	X	X	X	X	X						X

ARMB										Follow-up					
Study Period		Baseline (Initial Visit)					Follow-up								
Visit	V0	V1	–	V2	–	V3	–	V4	–	V5	1 mo post wean	–	3 mo post wean	–	6 mo post wean (Final visit)
Consent	X														
Eligibility Criteria	X														
NICU Discharge Summary	X														
Clinic O2 setting/Home Oximetry Data	X	X	X	X	X	X	X	X	X	X					
PedsQL	X	X	X	X	X	X	X	X	X	X			X		
Growth Assessment	X	X	X	X	X	X	X	X	X	X					X
AE/ED/Rehospitalizations		X	X	X	X	X	X	X	X	X			X		X
Nutrition Assessment	X	X	X	X	X	X	X	X	X	X					X
Home Ox Feasibility Questionnaire*											X*				

\*Home Oximetry Feasibility Questionnaire will be collected at the 1 month post wean follow-up visit. However, If a patient is missed or lost to follow-up, research staff may call the family to obtain this information as soon as possible before their last visit.

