**- Post Wean Follow- Up visits:**

The Post-Wean follow- up (f/u) visits are at 1 month, 3 month and 6 month after the patient has been weaned off oxygen.

- 1 month post-wean f/u visit: At the 1 month post wean visit, growth parameters, nutrition notes and will be collected. For ARM B patients only, a **post study Home Oximetry Feasibility Questionnaire** will be given to parents to complete. This questionnaire would be conducted at the 1 month post-wean visit, however, if unable to obtain at this time point, due to missed visit or lost to follow-up it can be collected post-wean at any time at a clinic visit or over the phone.
- 3 Month post-wean f/u visit: At the 3 month post-wean visit, a **PedsQL will be obtained. If unable to complete at this time, study staff at BCH or UMass will contact to obtain the survey over the phone.**
- 6 month post-wean f/u visit (Final Visit): At the 6 month post-wean visit, growth parameters and nutrition notes will be collected. In addition, the provider will inquire about respiratory-related hospitalizations or emergency department visits that may have occurred since oxygen discontinuation. Medical records will be reviewed to confirm this data. This visit marks the completion of participation in the study

Study staff will complete a final disposition form for every subject as a way to declare them officially off of the study.

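### The co-primary PedsQL analysis is set at 6 months after oxygen is stopped, but the only post-wean PedsQL is scheduled at 3 months, and no primary score is designated

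*Combined protocol and SAP*

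**What the plan says.** Section 4e makes parent quality of life primary measure (b), defined as "Parent quality of life, assessed by differences in the post-weaning PedsQL baseline". It gives no month after weaning and no total, summary or domain score.

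The analysis is in section 5d, Analyses for Aim 1 (Specific Aim 2 in the Abstract). A baseline is taken at the start of outpatient oxygen management. The study "then will repeat these measures at the end of the HOT weaning process (6 months after discontinuation of HOT"), and Student's t-test compares the arms on change in each measure. Regression models then adjust for parent and medical attributes. Hypothesis 1.1, in the same section, speaks of "improved quality of life compared to their status at time of NICU discharge". The power statement says it rests on the primary t-test. It gives 130 for 80% power at two-sided 0.05 to detect a 20% absolute difference in emotional role limitation. It gives no SD.

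Collection is described elsewhere. The Abstract says "A follow-up PedsQL will be done 3 months after weaning either by phone or at a clinic visit". Section 4d, item 1, has "a 3 month post weaning follow-up PedsQL report/survey either by phone or in clinic". Section 4f, Post Wean Follow-Up visits, puts the survey at the 3-month visit.

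The Abstract names the instrument as the PedsQL Family Impact Module. Study Procedures describes 36 items in eight health domains, each scored 0 to 100, and says the measures may be augmented with the Parent Advisory Board. The Baseline Visit text cites reference 38, which is an SF-36 manual.

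**The concern.** A primary analysis needs a fixed time point, a fixed score and an identified instrument. Here the analysis text asks for a measurement that the visit schedule does not contain. The endpoint definition that should settle the matter names neither the month nor the score. Whoever writes the final analysis would have to decide both, possibly after seeing data by arm.

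The time-point wording leaves some room. It refers to the end of weaning as well as to 6 months, and the PedsQL is also collected monthly until weaning. An analyst could therefore argue for the last survey on oxygen or for the 3-month survey. On the score, the analysis text tests each measure, does not say what a measure is, and has no rule for which result is primary.

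**Working it through.** **Time point.** The passages side by side:

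| Place | Post-wean PedsQL |
|---|---|
| 5d, Analyses for Aim 1 | 6 months: "then will repeat these measures at the end of the HOT weaning process (6 months after discontinuation of HOT" |
| Abstract | 3 months: "A follow-up PedsQL will be done 3 months after weaning either by phone or at a clinic visit" |
| 4d, item 1 | 3 months: "a 3 month post weaning follow-up PedsQL report/survey either by phone or in clinic" |
| 4f, 3-month visit | 3 months: "PedsQL will be obtained. If unable to complete at this time, study staff at BCH or UMass will contact to obtain the survey" |
| 4f, 6-month visit | none: "At the 6 month post-wean visit, growth parameters and nutrition notes will be collected", plus an enquiry about respiratory hospitalizations and ED visits |
| 4f, Arm B schedule | marked at 3 months, blank at 6 |
| 4e | no month given |

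The Arm A schedule is displaced in the extracted text. It shows a single post-wean PedsQL mark, and nothing here relies on its column. Count: one post-wean PedsQL at 3 months, none at 6.

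**Baseline.** Hypothesis 1.1 refers to NICU discharge. The informed consent text says "Consent will be obtained at the first study visit at all sites", and the first PedsQL is taken at that visit. The 5d analysis text agrees with the first visit, so only the hypothesis wording is out of line.

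**Score.** 4e names none. Study Procedures describes domain scores and no total. The 5d analysis text says each measure, and the 5d power statement says one domain.

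**Instrument.** Three descriptions need to be reconciled: the Family Impact Module (Abstract), 36 items with role-limitation domains (Study Procedures), and the SF-36 manual (Baseline Visit, reference 38). The emotional role limitation domain used for power is supported only by the 36-item description.

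**Power.** The figure of 130 cannot be reproduced because no SD is given, but the SD can be back-solved. Assume that 20% absolute means 20 points on the 0 to 100 scale. Then SD = 20 / [(z₀.₉₇₅ + z₀.₈₀) × √(2/n)].

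- 130 as a total (n = 65 per group): 20 / (2.802 × 0.1754) = 20 / 0.4914 = 40.7, or 40.4 with the noncentral t.
- 130 per group: 20 / (2.802 × 0.1240) = 20 / 0.3475 = 57.5.

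The first reading fits the 196 infants planned. The second would need 2 × 130 = 260. The documents do not say which is meant.

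Taking 130 as a total and SD 40.4, power is 93% with 98 per group. It is 89% with 83 per group (0.85 × 98 = 83.3, borrowing the completion rate that Table 2 states for duration of HOT). Power stays at 80% or more up to an SD of 49.7 with 98 per group, or 45.7 with 83.

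**The case against.** The strongest reply is that the conflict is one parenthesis in 5d against a consistent collection plan. 4e says post-weaning, only one post-wean survey exists, and it will be collected in both arms. This stands as far as it goes: the sensible reading is 3 months and the correction is short. It does not remove the defect, because the only passage that specifies the primary analysis asks for a different month, and 4e does not overrule it.

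A second reply is that the score is less open than it looks, since the power statement ties the primary t-test to one domain. That narrows the gap but does not close it. A domain mentioned only in a power sentence is not a designated endpoint, the analysis text in the same section says each measure, and the documents do not show that the named instrument yields that domain.

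A reader might infer more than the documents support:

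- *The quality-of-life data are lost.* They are not. The baseline and 3-month surveys are scheduled.
- *There is no usable baseline.* The 5d analysis text gives the start of outpatient management, which matches the first clinic visit.
- *The analysis runs eight tests at 0.05.* If each measure meant the eight domains, the chance of at least one false positive would be 1 − 0.95⁸ = 34% under independence, and 30%, 25% or 19% at assumed common correlations of 0.3, 0.5 or 0.7. But 5d does not say domain, and the phrase follows mentions of scales, so it may mean questionnaires. These figures are illustrative only and carry no weight in the conclusion.
- *The trial is underpowered for the PedsQL.* No shortfall is shown. The missing SD is a reporting gap.

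**Conclusion.** The point holds. One of two primary outcomes has an analysis time point at which no data are scheduled, an endpoint definition with neither month nor score, and an instrument identified in three ways that do not agree. The time-point and baseline findings need no assumption: they follow from setting the sections side by side.

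The consequence is a primary analysis that cannot be run as written and a primary score still to be chosen. It is not lost data and not an invalid test, since a t-test on change is a valid comparison of randomized arms. The power figures depend on three assumptions: 20% means 20 points, 130 is a total, and 85% completion applies to the PedsQL. If 130 were per group, the planned 98 would fall short of the stated 80% at the implied SD. That is a reason to state which is meant, not evidence of a shortfall.

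**What to change.** 1. **Time point and baseline.** Have the sponsor confirm that 3 months was intended. Then restate 4e and 5d so that the primary comparison uses the 3-month post-wean PedsQL with the first clinic visit as baseline, and align the NICU-discharge wording in hypothesis 1.1.
2. **Instrument, then score.** Reconcile the instrument's name (Abstract), description (Study Procedures) and citation (Baseline Visit, reference 38). Only then designate in 4e one primary score which that instrument yields. Label all other scores secondary, including any added with the Parent Advisory Board.
3. **Power.** Restate the calculation for that score with its SD and source, say whether 130 is a total or per group, and give power for the 98 per group now planned with expected completion.

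Optional, at no cost in data: make the primary comparison a linear model of the 3-month score on arm, baseline PedsQL and site (the blocking factor). The regression already planned in 5d names neither baseline PedsQL nor site. Any gain in precision depends on a baseline-to-follow-up correlation that the documents do not give.

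The cost is wording and a restated power statement. No new visits, patients or measurements are needed, and designating one score settles which PedsQL result is primary without splitting alpha across scores.

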**TABLE 2**

The power of detecting an effect of RHO on duration of HOT, indexed by the enrolled sample size and the difference in mean duration between the RHO and standard oxygen management group, assuming 85% completing all components of the study, a standard deviation of 66 days, and testing at the 2-tailed .05 level.

Difference in duration of HOT (days)	Enrolled n per group (double for total sample size)				
	33	44	53	60	98
30	45%	57%	65%	70%	89%
36	60%	73%	80%	85%	97%
49	85%	94%	97%	98%	>99%

*Analyses for Aim 3:*

Aim 3: To evaluate the extent to which a data-driven HOT managing protocol can improve growth and respiratory outcomes.	Hypothesis 3.1: Patients weaned from HOT using a data-driven protocol will have improved growth and decreased respiratory rehospitalizations compared to patients weaned using the current standard HOT weaning protocol.
--	--

The incidence of emergency department visits during HOT management process is estimated to be 30% in the RHO group and 40% in the standard weaning protocol. The two rates will be considered clinically noninferior if the difference was 10 percentage points or less (with a significance threshold of P=0.05 on a one-tailed test and 80% statistical power). On this basis, the number of patients required for each of the two treatment groups was calculated to be 65. With 98 patients per group the power increases to 93%.

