## **1. Abstract**

This research protocol describes a randomized control trial to compare two different methods of managing home oxygen therapy in premature infants. This is a multicenter study involving 9 centers. We plan to enroll a total of 196 infants, of which 68 will be from Boston Children's Hospital (BCH). The current standard for oxygen management includes brief assessments of a patient's oxygen saturation status during monthly clinic visits. The patient's oxygen status between visits is assumed to be acceptable; although it is possible for significant hyperoxia or hypoxia to occur, providers have no data to help with decision-making. In many centers, final steps before discontinuing home oxygen therapy (HOT) often include polysomnography (PSG), which can be costly and requires the inconvenience of rehospitalization. Advances in data storage and pulse oximetry technology have expanded potential uses for recorded home oximetry (RHO) in the accurate assessment of hypoxemia. At Boston Children's Hospital, we have pioneered the use of recorded home oximetry (RHO) in other research protocols, and shown that it can be a simple and convenient method for parents to transmit oximetry data to providers.

In this trial, we will randomize premature infants who require HOT at time of discharge from the NICU, who are referred for follow-up at the Center for Healthy Infant Lung Development. At the time of their first outpatient appointment, infants will be randomized to one of two treatment arms:

**Arm A (“Standard therapy”):** Infants' oxygen will be increased, decreased, or maintained based on brief structured assessments during monthly clinic visits. Polysomnograms will be utilized prior to final discontinuation of oxygen. RHO will only be utilized on the night prior to and during the polysomnogram to compare these two modalities.

**Arm B (RHO):** Infants will have the same monthly clinic assessments as in Arm A, but also will utilize RHO to potentially increase, decrease or maintain oxygen between monthly visits. Parents will transmit a minimum of 25 hours (1500 minutes) of stored RHO data (approximately 4 days, 8 hours per day) every 4-7 days. Changes in oxygen needs will be made based on standardized objective criteria. To determine discontinuation of oxygen, RHO will be utilized instead of polysomnography.

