**g. Study Timeline (as applicable)**

We expect to enroll the total of 68 patients from BCH over a 3.5-year period. (This is a multicenter study. Total enrollment will be 196 infants. We anticipate that our final patients will complete oxygen weaning after 6 months and 6-month follow-up for final outcomes assessment will be within 3 years of starting this project.

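### Table 2 says it allows for 85% completion, but its power figures use every enrolled infant; with the 85% applied, the 97% headline is about 94%.

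*Combined protocol and SAP*

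**What the plan says.** Duration of home oxygen therapy is one of two primary measures (section 4e), measured "from the first outpatient pulmonary appointment to discontinuation of supplemental" oxygen.

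Section 5d, under the analyses for Aim 2, expects a mean of 144 days (SD 66) with standard management and a reduction of 36 days with recorded home oximetry. It concludes: "A total sample of 98 infants per group provides 97% power to detect this effect of the RHO strategy". The reader is referred to Table 2.

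Table 2 has three rows (differences of 30, 36 and 49 days) and five columns (33, 44, 53, 60 and 98). The column heading reads "Enrolled n per group (double for total sample size", and the caption also says the table is indexed by enrolled sample size. The caption then lists the assumptions: "assuming 85% completing all components of the study, a standard deviation of 66 days, and testing at the 2-tailed .05 level".

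The Abstract states "We plan to enroll a total of 196 infants", and the Study Timeline repeats it: "Total enrollment will be 196 infants".

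**The concern.** A table indexed by enrolment that assumes 85% completion should base each cell on 0.85 times the column figure. The cell for 36 days and 98 per group looked too high for about 83 analysed infants per group and about right for 98.

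If so, the caption tells the reader that a 15% loss is already covered when none is. The stated power for a primary outcome would not follow from its own inputs. Anyone using the smaller columns to judge a recruitment shortfall would also be misled.

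**Working it through.** **Inputs.** SD 66 days, two-sided alpha 0.05, 85% completing, and enrolled n per group of 33, 44, 53, 60 and 98 (all Table 2). Equal allocation (block randomisation within site, section 4f). Comparison of two means (section 5d).

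**Formula.** With n analysed per group and difference Δ,

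Power = Φ(Δ/66 × √(n/2) − 1.96).

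**Step 1: reproduce the printed headline.** Take Δ = 36 and n = 98, with no loss. Then 36/66 × √49 = 3.818, less 1.96 = 1.858, and Φ(1.858) = 96.8%. The table prints 97%.

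**Step 2: apply the caption's 85%.** n = 0.85 × 98 = 83.3. Then 36/66 × √41.65 = 3.520, less 1.96 = 1.560, and Φ(1.560) = 94.1%. For Δ = 30 the same n gives Φ(0.974) = 83.5%, against 89% printed.

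**Step 3: all cells.** Each entry is printed / computed on 100% of enrolled / computed on 85% of enrolled, in percent.

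| Difference | 33 | 44 | 53 | 60 | 98 |
|---|---|---|---|---|---|
| 30 days | 45 / 45.48 / 39.8 | 57 / 56.8 / 50.2 | 65 / 64.8 / 57.8 | 70 / 70.2 / 63.1 | 89 / 88.9 / 83.5 |
| 36 days | 60 / 60.1 / 53.3 | 73 / 72.5 / 65.5 | 80 / 80.2 / 73.5 | 85 / 84.8 / 78.7 | 97 / 96.8 / 94.1 |
| 49 days | 85 / 85.45 / 79.4 | 94 / 93.6 / 89.4 | 97 / 96.9 / 94.1 | 98 / 98.2 / 96.3 | >99 / 99.9 / 99.8 |

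The 100% figures round to every printed cell. At 85%, 14 of 15 printed cells are too high. The smallest excess is 98 − 96.3 = 1.7 points (49 days, n = 60) and the largest is 73 − 65.5 = 7.5 points (36 days, n = 44). Only the >99% cell stays correct.

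**Step 4: which completion rate was used?** Of the 14 cells printed as exact percentages, the number reproduced to the printed percent is 0 at 85%, 0 at 90%, 1 at 95%, 9 at 99% and 14 at 100%.

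**Step 5: alternative explanations.**
- *Exact t-test.* With 83 whole completers per group, the noncentral t gives 93.7% for 36 days and 82.9% for 30 days. The normal approximation gives 94.0% and 83.4%. The choice of method does not account for the gap.
- *Columns are completers.* Then 98 completers would need 98/0.85 = 115.3, so 116 enrolled per group. This contradicts the column heading and the total of 196 = 2 × 98.
- *One-sided 0.05 at 85%.* This gives 97.0% for the headline, but it misses 8 of the 15 cells by more than 2 points and contradicts the stated two-tailed test.

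**Step 6: if loss for duration is smaller.** Assume 90% to 95% of durations are available (an assumption; the documents give no figure). Then 98 enrolled per group gives 95.2% to 96.1% for 36 days and 85.5% to 87.3% for 30 days, still below the printed 97% and 89%.

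**The case against.** The strongest reply is that the 85% may not belong to this endpoint. The caption speaks of completing everything in the study, and that runs to the visit 6 months after weaning, of which section 4f says "This visit marks the completion of participation in the study". Duration is known once oxygen stops, so an infant who later misses a questionnaire or the final visit still contributes. On that reading the fault is a misplaced phrase, and the true power lies somewhere between 94% and 97%. This stands as a limit on the replacement figure: the documents do not say which part is the mistake. It does not remove the inconsistency, because the caption lists the 85% among the inputs to this table and no cell reflects it.

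The second reply is that little depends on it. Twelve of the 15 cells are for sizes the trial does not plan to use. In the 98 column only two cells change, and both stay above 80%. That is correct, and it is why this is a correction to stated figures and not a challenge to the sample size. The smaller columns would matter only if recruitment fell short. There, three cells printed at 80% or more drop below it: 36 days with 53 and with 60 per group, and 49 days with 33 per group.

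**Conclusion.** The concern holds. Table 2 was computed with no loss, although its caption says 85% completion is assumed. Under the caption as written, 98 enrolled per group (about 83 completing) gives about 94% power for a 36-day difference in means, not 97%, and about 83% for 30 days, not 89%. The 49-day cell remains above 99%.

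These figures rest on the plan's SD of 66 days, equal groups, a two-sided 0.05 test, and the 85% applying to duration. If fewer durations are lost, power lies between these values and the printed ones. The planned enrolment remains adequate by the usual 80% standard for both differences, so the design and the analysis are unaffected.

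**What to change.** Recompute Table 2 on 0.85 × enrolled n, and restate the headline in section 5d along these lines: 98 enrolled per group, about 83 of them completing, gives about 94% power for a 36-day difference in mean duration and about 83% for 30 days. If the sponsor expects less loss for duration than for the whole study, state that rate in the caption and compute the table from it; showing power with and without loss would also be clear. Keep 98 labelled as enrolled.

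In the same edit, correct a small wording point. The headline sentence expects the intervention to "decrease the median duration by 25% (36 days) to 108 days", while the 144 days it starts from, Table 2 and the planned comparison all concern means. Changing the word to mean does not alter any power figure.

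The cost is a table and text correction. No extra infants and no change of analysis are needed; the stated power becomes slightly less favourable.
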